4. POPULATIONS (ANALYSIS SETS) FOR ANALYSIS

Vaccine assignment will be analyzed according to an as-treated principle. The analysis sets that are used for the various analyses are described in [Table 5](#).

Table 5 Analysis Sets

Analysis Sets	Description
Enrolled	The enrolled analysis set includes all participants who signed the ICF and who were not screen failures
Randomized	The randomized analysis set includes all participants who were randomized in the study.
Full Analysis Set (FAS)	All randomized participants with a documented study vaccine administration, regardless of the occurrence of protocol deviations and serostatus at enrollment.
Per Protocol Efficacy Set (PP; primary efficacy analysis set for vaccination studies)	Participants in the FAS who received double-blind study vaccine and who were seronegative at the time of double-blind vaccination and who have no major protocol deviations that were judged to possibly impact the efficacy of the vaccine. Participants who became aware of their study vaccine allocation will cease to be part of the PP population. See below for a definition.
Per Protocol Immunogenicity Analysis Set (PPI)	All randomized and vaccinated participants, including those who are part of the Immuno Subset and for whom immunogenicity data are available, excluding participants with major protocol deviations expected to impact the immunogenicity outcomes. In addition, for participants who experience a SARS-CoV-2 event (molecularly confirmed), samples taken after the event and samples taken outside protocol windows will not be taken into account in the assessment of the immunogenicity. The PPI population is the primary immunogenicity population. For key tables, sensitivity immunogenicity analyses will also be performed on the FAS, including participants who are part of the Immuno Subset for whom immunogenicity measures are available. Excluded samples might be taken into account as well in the sensitivity analysis. Analyses of vaccine immunogenicity and immune correlates of risk will be based on PPI.

For the PP the following additional criteria will be applied:

- having received the double-blind vaccine according to the randomization schedule
- having received at least 80% of the scheduled double-blind vaccination volume (according to the administration log)
- met inclusion criteria 1 (informed consent was obtained)

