5.2.2. COVID-19 case classification relevant definitions

Definitions relevant to COVID-19 case classification are listed below.

- **Episode** (of COVID-19): An episode of COVID-19 is defined as the period of the onset of (COVID-19) symptoms up until resolution of the episode. The severity of a COVID-19 will be determined based on the maximum severity observed across the episode.
- **Onset of (COVID-19) symptoms:** This is the date when any sign(s) or symptom(s) suggesting possible COVID-19. It will be called Day 1 of an episode. It is the earliest date the first symptom of an episode entered on the eCOA or on the CRF if entered by the site (“*If a participant records in the eCOA or informs the site that he/she experienced any signs or symptoms suggesting possible COVID-19, this will be considered COVID-19 Day 1 (day of onset of signs and symptoms).*” CTP) or the AE onset date if linked to COVID-19 (The following preferred terms are included in this analysis: "COVID-19", "ASYMPTOMATIC COVID-19", "SUSPECTED COVID-19", "COVID-19 PNEUMONIA" and "SARS-COV-2 TEST POSITIVE"). [Day 1 will be derived based on the first symptoms that are entered in the eCOA before the first swab is taken. In case there are multiple days with symptoms entered in the eCOA before the first swab, Day 1 is the earliest Day of all consecutive Days with signs or symptoms that are at least mild. Days without symptoms within 7 days before the first swab will be ignored in the evaluation of consecutive days.] A sensitivity analysis will be done to evaluate the change in onset date based on the 7 day window compared to the algorithm implemented at the primary analysis, where a day without symptoms interrupted the consecutive Days.
- **Resolution of an episode:** Resolution of the COVID-19 episode is defined as having 2 consecutive SARS-CoV-2 negative nasal swabs and 2 consecutive days with no COVID-

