For the evaluation of the immune response in participants with COVID-19 in relation to risk of development of COVID-19, protection induced by Ad26.COV2.S, and risk of accelerated disease by assessment of the correlation of humoral immune responses with emphasis on neutralizing, binding and functional antibodies, as well as gene transcript profiling (RNA sequencing), with the risk of COVID-19 and protection induced by the study vaccine participants with a COVID-19 episode immunogenicity data will be tabulated by vaccine regimen at baseline, 28 days post double-blind vaccination, on COVID-19 Day 3-5 and on COVID-19 Day 29 for the standard immunogenicity assays (S-ELISA and VNA) and on COVID-19 Day 3-5 and on COVID-19 Day 29 for all other assays that are available ([Table 9](#)). Immunogenicity data will be graphically displayed by vaccine regimen where actual values are shown as dot plots with dots for participant values, and the corresponding geometric mean and 95% CI per time point for each assay. Correlates will be assessed in a subset where immune responses and transcriptome modifications are measured in all vaccine recipients who experience a SARS-CoV-2 event, and in random samples of vaccine recipients who have not been infected. These analyses will be described in a separate correlates SAP for this purpose.

For the assessment of the humoral immune response to Ad26.COV2.S, as compared to placebo for functional and molecular antibody characterization including, but not limited to avidity, Fc-mediated viral clearance, Fc characteristics, Ig subclass, IgG isotype, antibody glycosylation, and assessment of antibody repertoire, adenovirus neutralization as measured by VNA and analysis of antibodies to the receptor-binding domain (RBD) of the SARS-CoV-2 S protein refer to section [5.8.1](#).

Changes in the SARS-CoV-2 genome are focused at analyses of the S protein sequence. The presence of predefined viral variants will be tabulated. Further detail on vaccine efficacy by viral variant is described in section 5.8.2.6. Sequence analyses will be reported in a separate report. Time to resolution of COVID-19 episodes will be described for participants in the Ad26.COV2.S and placebo groups, using the Kaplan-Meier methodology, and if applicable compared with a logrank test.

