5.8.2. Immunogenicity

Blood will be collected from all non-Immuno Subset participants for humoral immunogenicity assessments before double-blind vaccination, 28 days after double-blind vaccination and at D71, W24 and W782 after double-blind vaccination. For a total of approximately 400 participants in the Immuno Subset, blood will be collected for analysis of humoral immune responses before double-blind vaccination, 28 days after double-blind vaccination, 70 days after double-blind vaccination, and 24, 52, 78, and 104 weeks after double-blind vaccination.

During a COVID-19 episode, blood will be collected on COVID-19 Day 3-5 and on COVID-19 Day 29 for immunogenicity assessments, including the assays summarized in [Table 9](#).

Table 9 Immunogenicity and Transcriptomic Assessments

Humoral Assays	Purpose
Supportive of Secondary Objectives	
SARS-CoV-2 binding antibodies to S protein (ELISA)	Analysis of antibodies binding to SARS-CoV-2 S protein
SARS-CoV-2 seroconversion based on antibodies to N protein (ELISA and/or SARS-CoV-2 immunoglobulin assay)	Analysis of antibodies binding to SARS-CoV-2 N protein
Supportive of Exploratory Objectives	
SARS-CoV-2 neutralization (VNA)	Analysis of neutralizing antibodies to the wild-type virus, and/or pseudovirion expressing S protein
SARS-CoV-2 binding antibodies to S protein (MSD)	Analysis of antibodies binding to SARS-CoV-2 S protein (different than the assays supportive of the secondary objectives) and the receptor-binding domain (RBD) of SARS-CoV-2 S protein
Functional and molecular antibody characterization	Analysis of antibody characteristics including, but not limited to, avidity, Fc-mediated viral clearance, Fc characteristics, Ig subclass, IgG isotype, antibody glycosylation, and assessment of antibody repertoire
Adenovirus neutralization (VNA)	Adenovirus neutralization assay to evaluate neutralizing antibody responses against the Ad26 vector
Binding antibodies to other coronaviruses (MSD)	Analysis of antibodies binding to coronaviruses other than SARS-CoV-2
Transcriptomic Assay	Purpose
Supportive of Exploratory Objectives	
Gene expression analysis	Analysis of gene expression by RNA transcript profiling in unstimulated cells or whole blood

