Ad26 = adenovirus type 26; ELISA = enzyme-linked immunosorbent assay; Fc = crystallizable fragment; Ig(G) = immunoglobulin (G); MSD = Meso Scale Discovery; N = nucleocapsid; RBD = receptor-binding domain; RNA = ribonucleic acid; S = spike; SARS-CoV-2 = severe acute respiratory syndrome coronavirus-2; VNA = virus neutralization assay.

The analysis of immunogenicity will use the PPI set.

For the non-immuno subset, humoral immunogenicity data will be analyzed according to the as-treated principle by vaccine regimen (active vaccine, placebo), by vaccine regimen and participant seropositivity status at screening and by vaccine regimen and COVID-19 (no infection, asymptomatic infection, mild, at least mild, at least moderate, at least severe) and by vaccine regimen and age and

comorbidity (with/without) strata, by vaccine regimen and country/region, by vaccine regimen and emerging CD4 count abnormality (at least grade 1 at any time after double-blind vaccination) and viral load (treatment emergent detectable viral load). Specific immunogenicity analyses will be performed on the Immuno Subset. All immunogenicity analyses for the immuno subset will be analyzed by vaccine regimen and by vaccine regimen and age and comorbidity (with/without) strata.

At the time of primary analysis, partially available immunogenicity data are summarized. Analysis will be updated when complete data available.

For participants with a COVID-19 episode immunogenicity data will be analyzed by vaccine regimen at baseline, 28 days post double-blind vaccination, on COVID-19 Day 3-5 and on COVID-19 Day 29 for the standard immunogenicity assays (S-ELISA and VNA) and on COVID-19 Day 3-5 and on COVID-19 Day 29 for all other assays that are available (Table 6).

Correlates will be assessed in a subset where immune responses and transcriptome modifications are measured in all vaccine recipients who experience a SARS-CoV-2 event, and in random samples of vaccine recipients who have not been infected. These analyses will be described in a separate correlates SAP.

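### The PPI rule drops every sample taken after a molecularly confirmed event, so the COVID-19 Day 3-5 and Day 29 summaries planned in SAP 5.8.2 have no usable samples from confirmed cases, and 5.6 points to a different analysis set for the same analysis

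*SAP*

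**What the plan says.** Section 4, Table 5 makes PPI the primary immunogenicity population. For participants with a molecularly confirmed SARS-CoV-2 event, "samples taken after the event and samples taken outside protocol windows will not be taken into account in the assessment of the immunogenicity". The same entry adds that "Analyses of vaccine immunogenicity and immune correlates of risk will be based on PPI". It allows sensitivity analyses on the FAS for key tables, in which excluded samples may be used.

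Section 5.8.2 schedules the episode samples: "During a COVID-19 episode, blood will be collected on COVID-19 Day 3-5 and on COVID-19 Day 29 for immunogenicity assessments". It then fixes the analysis set: "The analysis of immunogenicity will use the PPI set". A few lines later it plans the episode analysis: "For participants with a COVID-19 episode immunogenicity data will be analyzed by vaccine regimen at baseline, 28 days post double-blind vaccination, on COVID-19 Day 3-5". These timepoints apply to S-ELISA and VNA, with COVID-19 Day 29 as the fourth. All other assays are to be summarised at the two episode timepoints only.

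Section 5.6.1.2 repeats the plan for the exploratory objective on immune response, protection and risk of accelerated disease, again "on COVID-19 Day 3-5 and on COVID-19 Day 29 for all other assays that are available". It names no analysis set. The opening of Section 5.6 gives the PP set, in seronegative participants, as the default for exploratory endpoints unless otherwise indicated.

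**The concern.** The exclusion in PPI has a sound purpose: it keeps antibody produced by infection out of the summaries of the response to vaccination. In the episode analysis, however, the response after infection is the quantity of interest, and the rule is triggered by the very event being studied. No sentence in Table 5, 5.8.2 or 5.6.1.2 exempts the episode samples.

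At stake is the descriptive comparison of vaccine and placebo recipients during a COVID-19 episode. A programmer must either apply the declared set and produce empty columns, or choose a set that the plan does not name for this purpose. The SAP introduction states that sponsor personnel were unblinded at the primary analysis, so that choice would now be made without the protection of blinding.

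**Working it through.** There is no figure to reproduce. The check applies the PPI sample rule to each timepoint of the episode analysis.

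Inputs:

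- Sample rule and its trigger (a molecularly confirmed event): Section 4, Table 5.
- Analysis set: PPI, from Section 5.8.2.
- Planned timepoints: Sections 5.8.2 and 5.6.1.2.
- Day count: Section 5.2.2 says of the onset of symptoms, "It will be called Day 1 of an episode". COVID-19 Day 3-5 is therefore 2 to 4 days after onset, and COVID-19 Day 29 is 28 days after onset.

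Result on PPI for a molecularly confirmed case:

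| Timepoint | S-ELISA and VNA | All other assays |
|---|---|---|
| Baseline | kept | not planned |
| 28 days post vaccination | kept if the event came later | not planned |
| COVID-19 Day 3-5 | excluded | excluded |
| COVID-19 Day 29 | excluded | excluded |

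The rule therefore removes 2 of 4 timepoints for S-ELISA and VNA, and 2 of 2 for every other assay. For those other assays the episode analysis is empty on PPI.

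Table 5 does not say how the event is dated. The table above dates it at symptom onset. If it were dated at the first positive swab, the result would change little: the viral-load entry in Section 5.5.3 has nasal swabs starting with the episode, so only a Day 3-5 blood sample drawn before a late first positive swab would escape. COVID-19 Day 29 would normally be excluded either way.

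Comparison of the two sections on the analysis set:

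- Section 5.8.2 uses PPI, which drops the episode samples of confirmed cases.
- Section 5.6 defaults to PP. The PP criteria in Section 4 contain no rule on samples taken after a confirmed event, so the episode samples stay. PP also excludes participants who were seropositive at baseline, which the PPI definition does not.

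The same analysis thus has different samples, and partly different participants, depending on which section is followed.

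The rule also reaches two other displays: the 5.8.2 summaries by COVID-19 status and the participant profiles over time for COVID-19 cases in 5.8.2.4.1. For confirmed cases, both would show pre-event values only.

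**The case against.** The strongest reply is that a specific instruction overrides a general one. Section 5.8.2 schedules blood at the two episode timepoints and names them for analysis, so the intent is plain, and a competent programmer would raise a query before producing blank tables. The closing sentence of the PPI entry speaks of vaccine immunogenicity, and the response to an infection is arguably something else. Both arguments bear on intent, and the intent is probably as described. They do not supply the missing exemption. Elsewhere the SAP writes one when it needs it: Sections 5.4.7 and 5.5.1 explain in a note how seropositive participants are handled in displays based on PP, which otherwise has none.

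A second reply is that the data can be reached by other routes, and this partly stands. Under the PP default of Section 5.6, the analysis in 5.6.1.2 does have episode samples. It can be answered that Table 5 and 5.8.2 otherwise indicate PPI for immunogenicity, but 5.6.1.2 does not say so, and the conflict remains. The FAS sensitivity analysis could also recover the samples, but it covers key tables only and the use of excluded samples is optional.

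A reader might infer that the whole episode analysis has no data, or that the look for accelerated disease is lost. The documents do not support that. Baseline values and pre-event 28-day values for S-ELISA and VNA survive on PPI. Monitoring for excess symptomatic and severe cases runs on the FAS under Sections 5.9.2 and 5.9.3 and does not use these samples. Correlates of risk are deferred to a separate SAP.

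**Conclusion.** The contradiction is real and confined. On the set that 5.8.2 names, the two in-episode timepoints have no usable samples from molecularly confirmed cases: half the planned timepoints for S-ELISA and VNA, and all of them for the other assays. For 5.6.1.2 the defect is a conflict over the analysis set, not an analysis that cannot be made.

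This rests on reading the PPI rule literally and on dating the event at symptom onset. It concerns molecularly confirmed events only; the rule does not touch samples from episodes without confirmation.

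The point is minor. Section 5.8.2.3 tests no formal immunogenicity hypothesis, the outputs are tables and plots, and neither an efficacy claim nor a harm boundary depends on them.

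**What to change.** In Table 5 or Section 5.8.2, state that the exclusion of samples taken after a molecularly confirmed event applies only to the scheduled-visit summaries of vaccine response, and not to the COVID-19 Day 3-5 and Day 29 timepoints. Keep the other PPI criteria, including the exclusion for major deviations, since they play no part in the conflict. In Section 5.6.1.2, name the same analysis set for this analysis so that the PP default of Section 5.6 no longer competes with it.

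The cost is one or two sentences and a flag on the sample records. The blood is collected in any case, and no other analysis changes. A wholly new population or added baseline-serostatus strata are not needed to resolve the contradiction.

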5. STATISTICAL ANALYSES

5.1. General Considerations

Unless otherwise indicated, all analyses will pool data across ages and with/without co-morbidities for evaluation without stratification.

Analysis adjusting for randomization factors will be explicitly mentioned when done and will include the age groups and with/without co-morbidities only.

Stratification for (mobile) site unit at the time of randomization was done to ensure balance in exposure to SARS-CoV-2 between randomized groups over time because of the spatiotemporal evolution of the epidemic. However, including all stratification factors (age by comorbidity by (mobile) site) in the analysis will result in a large number of ‘empty strata’ (i.e. without cases) as the TNE of 154 is substantially lower than the anticipated number of stratification levels. Therefore no summaries will be provided by this stratification factor (mobile unit).

The final analysis planned at the end of the double blind phase, comparing vaccine versus placebo, will include efficacy and safety data collected during the ‘double blind phase’ of the trial, i.e. with an onset date of the event (or censor date) up to unblinding date.

To include the available data after unblinding, this analysis – comparing vaccine versus placebo – will be supplemented for primary and secondary endpoints with an analysis evaluating all available events until study discontinuation or upon administration of another authorized/approved vaccine up to the data lock point. Events that occurred after cross-over to another COVID-19 vaccine (including the Janssen Vaccine if received outside of the study) will be tabulated separately.

The analysis of the open-label phase (comparing efficacy between immediate vaccination versus delayed vaccination with the Janssen COVID-19 vaccine during the open-label phase of the study will include efficacy and safety data after unblinding and will be described in a separate SAP. Per protocol amendment 5, this analysis is planned when all subjects had at least one year of follow-up.

5.1.1. Study Phases

A baseline (or reference) value will be defined as the value of the last available assessment prior to the vaccination on Day 1.

The safety analysis will present all results by study phase (see Section 5.1.2). Immunogenicity results will be presented per scheduled time point as appropriate. Listings will be shown per phase and time point.

Study day or relative day is defined as follows:

- Study Day = visit date – date of Day 1 + 1; if visit date \geq date of Day 1 (date of first vaccination).
- Study Day = visit date – date of Day 1; if visit date $<$ date of Day 1 (date of first vaccination).

5.1.2. Phase Definitions

The phases in the study will be constructed as follows:

Table 6 Phase Definitions for Double-Blind Safety Analysis

Phase	Phase #	Period	Period #	Interval	
				From	To
Screening	1			Date and time of signing the informed consent form	One minute prior to start of post dose 1 period
Post-dose	2	Post-dose	1	Date and time of first vaccination	Minimum of: a) 23:59 at the date of last contact (for early discontinuation)

Statistical Analysis Plan VAC31518COV3001

				
 b) 23:59 at the date of data base cut-off date in case of interim c) 23:59 on 28 days after the first vaccination (23:59 of day of vaccination + 28 days) d) One minute before date and time of treatment unblinding e) One minute before date and time of another vaccination outside the study
Follow-up (D30-M6)	3		One minute after Post-dose 1 Period end	
Minimum of:
 
 a) 23:59 at the date of last contact (for early discontinuation) b) 23:59 at the date of data base cut-off date in case of interim c) 23:59 at date of the Month 6 (date of vaccination + 6 Months) d) One minute before date and time of treatment unblinding e) One minute before date and time of another vaccination outside the study
Follow-up (M6-W52)	4		One minute after Follow-up (D30-M6)	
Minimum of:
 
 a) 23:59 at the date of last contact (for early discontinuation) b) 23:59 at the date of data base cut-off date in case of interim c) One minute prior to Week 52 Visit d) One minute before date and time of treatment unblinding e) One minute before date and time of another vaccination outside the study
Long term Follow-up (W52-End)	5		One minute after Follow-up (M6-W52)	
Minimum of:
 
 a) 23:59 at the date of data base cut-off date in case of interim b) maximum of: 
 1. 23:59 at the date of last contact (for early discontinuation) 2. 23:59 at the date of last visit

Statistical Analysis Plan VAC31518COV3001

					
 3. One minute before date and time of treatment unblinding 4. One minute before date and time of another vaccination outside the study
Open label Follow -up 1	6			Date and time of unblinding	
Minimum of
 
 a) 23:59 at the date of data base cut-off date in case of interim b) One minute prior to date and time of second/other vaccination within or outside the study c) Maximum of: 
 1. 23:59 at the date of last contact (for early discontinuation) 2. 23:59 at the date of last visit
Follow-up other vaccine	7			Date and time of vaccination outside the study	
Minimum of
 
 a) 23:59 at the date of data base cut-off date in case of interim b) Maximum of: 
 1. 23:59 at the date of last contact (for early discontinuation) 2. 23:59 at the date of last visit

Table 7 Phase Definition for Pooled Open Label Safety Analysis

Phase	Phase #	Period	Period #	Interval	
				From	To
Post Dose	1	Post dose	1	Date and time of Ad26.COV.2 vaccination	
Minimum of
 
 a) 23:59 at the date of data base cut-off date in case of interim b) One minute before date and time of another vaccination outside the study c) 23:59 on 28 days after the first vaccination (23:59 of day of vaccination + 28 days) d) 23:59 at the date of last contact (for early discontinuation)
Follow-up (D30-M6)	2			One minute after Post-dose 1 Period end	Minimum of:

					
 a) 23:59 at the date of last contact (for early discontinuation) b) 23:59 at the date of data base cut-off date in case of interim c) 23:59 at the date of the Month 6 (date of Ad26.COV.2 vaccination + 6 Months) d) One minute before date and time of another vaccination outside the study
Follow-up (M6-W52)	3			One minute after Follow-up (D30-M6)	
Minimum of:
 
 a) 23:59 at the date of last contact (for early discontinuation) b) 23:59 at the date of data base cut-off date in case of interim c) One minute prior to Week 52 Visit d) One minute before date and time of another vaccination outside the study
Long term Follow-up (W52-End)	4			One minute after Follow-up (M6-W52)	
Minimum of:
 
 a) 23:59 at the date of data base cut-off date in case of interim b) maximum of: 
 1. 23:59 at the date of last contact (for early discontinuation) 2. 23:59 at the date of last visit 3. One minute before date and time of another vaccination outside the study

Under protocol amendment 3 and 4, subjects in the placebo arm may receive the active vaccine (or another authorized vaccine). For the purpose of the safety analysis, the post dose period of the double blind phases refer to the first vaccination either with placebo or active vaccine. The post dose of the open label pooled phases refer to the active vaccination, which will be the first vaccination for the active group and the second vaccination for the placebo group after unblinding. The Open-label Pooled phases, are defined only for subjects that received a Ad26.COV.2 vaccination and start from the date that they received their Ad26.COV.2 vaccination.

When the time of the first vaccination is missing and it occurred on the same day as the randomization, the time of vaccination will be imputed with the time of randomization Otherwise,

if the date is available of the first vaccination then the time will be imputed with 00:00 before applying the phase and period derivation rules.

In case the time of the second vaccination or the vaccination outside the study is missing then time will be imputed with 00:00 if the date is available. In case of a partial date and the second vaccination or the vaccination outside the study occurred after the unblinding date, then the available info will be compared to the unblinding datetime. If the month is available and it is the same as the unblinding month then the day is imputed with the day of the unblinding. If the month is after the month of unblinding then the day is imputed with the first of that month. If the month and day are missing then the year will be compared with the year of unblinding. If the year is the same then the month and day are imputed with the day and month of the unblinding date. If the second vaccination or the vaccination outside the study occurred before being unblinded then the partial date will be compared in a similar way to the first vaccination datetime. In case the time of the unblinding datetime is missing then the time is imputed with 23:59.

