Safety analyses will be performed on the FAS. No formal statistical testing of safety data is planned. Safety data by double-blind vaccination group will be analyzed descriptively. Specific safety analyses will be performed on the Safety Subset. All safety analyses will be tabulated by treatment group (active vaccine, placebo) according to the as-treated principle. All safety analyses will be presented overall and by age and comorbidity (with/without) strata. The main age strata for reporting purposes are ≥ 18 to < 60 years of age and ≥ 60 years of age. In addition, safety data will be analyzed by treatment group and participant seropositivity status at screening.

For the double-blind phase, the safety data up to the unblinding date will be presented separately for the Ad26.Cov 2 double-blind group and the placebo double-blind group (Analysis I). Safety data after the unblinding date but before the open label vaccination date are listed separately.

Additionally, safety data will be pooled for all subjects that received Ad26.Cov 2 (in the double blind phase or in the open label phase) from the start of their Ad26.Cov 2 vaccination to the end of the trial (Analysis II): unsolicited AEs up to day 28, SAEs and MAAEs leading to discontinuation during the entire study, MAAEs until 6 months after last vaccination, AEs of special interest and AEs of interest during the entire study. All tables will be presented by phase.

The safety data from subjects that were unblinded and who received a vaccine outside the study will be tabulated separately.

Subjects that took another COVID-19 vaccine before being unblinded are excluded from the safety tables from the moment they received the other vaccine. The safety data from those subjects after they received the other vaccine are listed separately.

Denominator for the percentages is the number of participants in the considered population and phase for a certain regimen (incidence per 100 participants/phase).

Continuous variables will be summarized using the following statistics, as appropriate: number of observations, arithmetic mean (mean), 95% CI for the mean, standard deviation (SD), median, quartiles (Q1 and Q3), minimum and maximum. Frequencies and percentages (one decimal place) will be generated for categorical variables. No formal comparisons between groups will be provided.

Other exploratory or sensitivity analyses may be performed in addition to the analyses described below on an ad-hoc basis.

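### In the last follow-up phase of Tables 6 and 7, the unblinding and outside-vaccination cut-offs sit inside a maximum and so do not end the phase for participants followed further

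*SAP*

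**What the plan says.** Table 6 (double-blind safety) ends phases 2 to 4 at the minimum of a list. Unblinding is a direct member of that list, "d) One minute before date and time of treatment unblinding", and outside vaccination follows as item e). Table 7 (pooled Ad26.COV2.S safety) treats outside vaccination the same way in phases 1 to 3.

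The long-term follow-up phase is built differently. In Table 6 phase 5 the end is the minimum of (a) the database cut-off and (b) a maximum of four items. Items 1 and 2 are last contact and last visit. Items 3 and 4 are "3. One minute before date and time of treatment unblinding" and "4. One minute before date and time of another vaccination outside the study". Table 7 phase 4 has the same shape, with "3. One minute before date and time of another vaccination outside the study" inside the maximum.

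Phase 5 starts one minute after phase 4 ends, and nothing is said about what ended phase 4. Phase 6 starts at "Date and time of unblinding". Its own end rule keeps the vaccination cut-off in the outer minimum and leaves only last contact and last visit in the maximum.

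Section 5.7 states the intended scope: "For the double-blind phase, the safety data up to the unblinding date will be presented separately". It also excludes data after another vaccine taken before unblinding and lists them separately, and it tabulates separately the data of unblinded participants vaccinated outside the study. Sections 5.1 and 5.1.5 likewise stop the double-blind analysis at unblinding.

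On missing times, Section 5.1.2 says: "In case the time of the unblinding datetime is missing then the time is imputed with 23:59". A missing time of the second vaccination becomes 00:00.

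**The concern.** A cut-off inside a maximum can only lengthen an interval. For anyone with a contact or visit after unblinding or after an outside vaccine, the later date wins and the cut-off has no effect. The long-term double-blind phase then covers open-label time, and the pooled Ad26.COV2.S phase covers time after a different vaccine.

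Section 5.7.1.3 allocates an adverse event to a period that contains its start, and Sections 5.1.1 and 5.7 present safety by phase with per-phase denominators. At stake is whether the randomised safety comparison contains only blinded exposure, and whether the pooled Ad26.COV2.S results are free of events after other vaccines. The outputs concerned cover the whole study: SAEs, AESIs and MAAEs leading to discontinuation.

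**Working it through.** The SAP gives no figure to reproduce. The check applies the end rules literally to example participants, then repeats them with the cut-offs in the outer minimum.

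**Inputs from the SAP:** the start and end rules of Tables 6 and 7 (Section 5.1.2); the cut-off of 9 July 2021 (Section 1); the study start of 21 September 2020 (Section 5.4.8).

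**Assumptions, for illustration only:** vaccination on 15 October 2020; Month 6 = day 183; Week 52 = day 364; follow-up to 9 July 2021 or to day 730.

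**Rules.** Let U be unblinding, O outside vaccination, C the cut-off, L last contact and V last visit.
- Phase 5 end as written: min{C, max(L, V, U − 1 min, O − 1 min)}.
- Phase 5 end as corrected: min{C, max(L, V), U − 1 min, O − 1 min}.
- Table 7 phase 4 is the same without U. Having no unblinding term there is proper, because the pooled phases are meant to run through unblinding.

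**After Week 52**
- *Unblinded on day 420, followed to day 730.* As written, phase 5 runs from day 364 to day 730, which is 366 days, of which 730 − 420 = 310 follow unblinding and overlap phase 6. Corrected, it lasts 420 − 364 = 56 days, less one minute.
- *Outside vaccine on day 400, not unblinded, followed to day 730.* As written, 730 − 400 = 330 days follow the other vaccine and overlap phase 7. Corrected, phase 5 lasts 400 − 364 = 36 days, less one minute.
- *Table 7, outside vaccine on day 400.* Again 330 days too long as written. Table 7 has no later phase to receive these events.

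**At the 9 July 2021 cut-off**
- From 21 September 2020 to 9 July 2021 is 291 days. Since 291 < 364, nobody can have reached Week 52.
- *Unblinded at 09:00 on 4 March 2021 (day 140).* Phase 3 ends at 08:59. Phase 4 would start at 09:00 and end at 08:59, so it is empty. If phase 5 then starts one minute after that end, it runs from 09:00 on 4 March to 9 July, 127 days, and overlaps phase 6 throughout. Corrected, phase 5 is empty.
- *Table 7, outside vaccine on day 150 (14 March 2021).* The same literal start rule gives a phase 4 of 117 days. Corrected, it is empty.

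**Same-day times.** If the unblinding time is missing and the cross-over dose is given that day, unblinding is set to 23:59 and the double-blind phase ends at 23:58, after the dose. If both times are missing, the dose is set to 00:00. Phase 6 then starts at 23:59 that day and ends at 23:59 the day before. The displacement is always under one day.

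**The case against.** The best reply is that the intent is clear. Sections 5.1, 5.1.5 and 5.7 all stop double-blind safety data at unblinding and set aside data after another vaccine, so a programmer would have to follow a table cell against several explicit rules. Phase 5 is also labelled W52-End, and nobody reaches Week 52 by 9 July 2021. If it opens only at Week 52, no record in this analysis is affected. Safety is descriptive, without formal testing.

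Most of this stands as a limit on size. It does not remove the contradiction. The tables are what gets programmed, and no text says that an empty phase cannot open the next one.

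A reader might infer four stronger things that the SAP does not support:
- **That 90% or more of participants receive a spurious phase in this analysis.** This needs the literal start rule after an empty phase 4. Section 1 also makes analysis at 90% unblinded an option; the plan is all participants unblinded or discontinued.
- **That MAAEs in general are affected.** Section 5.7.1.1 limits those outputs to Post-dose through M6-W52, which excludes phase 5.
- **That events move out of their proper phase.** Phases 6 and 7 still open, so the phase 5 allocation is additional. After an in-study cross-over dose phase 6 has closed, but the event still belongs to the pooled phases of Table 7.
- **That phases 2 to 4 of Table 6 are wrong.** Their minimum is sound; only the same-day imputation touches them.

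**Conclusion.** The defect holds as an internal contradiction. The end rules of Table 6 phase 5 and Table 7 phase 4 disagree with the other phases of the same tables, with the structure of phase 6, and with Sections 5.1, 5.1.5 and 5.7. It does not look like a text-extraction artefact: the items continue the numbering of the inner list, and both tables share the pattern.

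Its size depends on when phase 5 opens. For participants followed past Week 52 the cut-offs fail to end the phase, whether it opens at Week 52 by its label or earlier by its start rule. In the examples the excess is 310 days after unblinding and 330 days after another vaccine. For the 9 July 2021 analysis the effect is conditional: none if phase 5 waits for Week 52, and 127 days (Table 6) or 117 days (Table 7) in the examples if the start rule is applied literally. These lengths rest on the assumed dates; the direction does not.

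The Table 6 consequence is extra allocation of whole-study events to a double-blind phase. The Table 7 consequence is that events after another vaccine remain in the pooled phase. The imputation flaw is real but separate and minor, and the SAP gives no frequency of missing times.

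**What to change.** 1. In Table 6 phase 5, move items 3 and 4 to the outer minimum, leaving only last contact and last visit in the maximum. In Table 7 phase 4, move item 3 likewise. This matches the structure of Table 6 phase 6.
2. State that a phase is created only if the previous phase ended on schedule (Day 28, Month 6, Week 52), and not through unblinding, other vaccination or discontinuation.
3. For same-day unblinding and cross-over, set an imputed unblinding time no later than the vaccination time, without moving it to the previous day, and end the double-blind phase no later than the cross-over dose. A rule of one minute before the dose would not work: with the dose time imputed as 00:00 it lands on the previous calendar day.

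The cost is a wording change and a small programming change to the phase derivation before the tables are produced. No new data are needed.
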